6.6.3 Other Safety Measurements

6.6.3.1 Columbia-Suicide Severity Rating Scale (C-SSRS)

The C-SSRS is routinely used to quantify the severity of suicidal ideation and behavior. Both the ideation and behavior subscales are sensitive to change over time.

The scale identifies behaviors that may be indicative of an individual's intent to commit suicide. This measure contains six "yes" or "no" questions in which respondents are asked to indicate whether they have experienced several thoughts or feelings relating to suicide over the past month. Each question addresses a different component of the respondent's suicide ideation severity: (1) Desire to be dead; (2) Suicidal thoughts; (3) Consideration of suicide methods; (4) Formed intent to commit suicide; (5) Completed suicide plan; and (6) Initiated suicide plan. A higher score indicates a higher intensity of suicidal ideation.⁴³

At the Screening Visit, the C-SSRS Baseline/Screening version will be administered. At all subsequent visits, the C-SSRS Since Last Visit version will be administered.

6.6.3.2 Clinician Administered Dissociative States Scale (CADSS)

The CADSS is an instrument for the measurement of present-state dissociative symptoms with good interrater reliability and construct validity. The CADSS can discriminate patients with dissociative disorders from healthy subjects and patients with other psychiatric disorders. The CADSS is a 23-item scale with all items administered to the subject. A higher score indicates a higher likelihood of the presence of a dissociative state. Subscales of the CADSS were developed to identify amnesia (Items 14 and 15), depersonalization (Items 3 to 7), and derealization (Items 1, 2, 8 to 13, and 16 to 19).⁴⁴

6.6.3.3 Clinical Opiate Withdrawal Scale (COWS)

Safety assessments have been included to monitor for any opioid-related effects. The COWS is a clinician-administered instrument that rates 11 common opiate withdrawal signs or symptoms. The summed score of the 11 items can be used to assess a patient's level of opiate withdrawal and to make inferences about their level of physical dependence on opioids.⁴⁵

6.6.3.4 4-Item Positive Symptom Rating Scale (4-Item PSRS)

The 4-Item PSRS was adapted from the Brief Psychiatric Rating Scale developed by Ventura and colleagues. It is a clinician-administered scale intended to assess the extent to which a subject is

currently experiencing positive psychotic symptoms. The scale assesses paranoia and hallucinations as well as some specific issues related to difficulty thinking and having unusual thoughts. When administering the scale, the rater enters a number for each of 4 symptom constructs with scores that range from 1 (not present) to 7 (extremely severe). Total score on the 4-Item PSRS can range from 4 to 28. ^{46,47}

6.6.4 Pharmacokinetic (PK) Assessments

Standard PK assessments, appropriate for an early Phase 2 study, have been included as outlined in Section 6.3.

7 ADVERSE EVENTS AND SERIOUS ADVERSE EVENTS

The Investigator or designee and research site staff are responsible for the detection, documentation, classification, reporting, and follow-up of events meeting the definition of an AE or SAE. Procedures for managing AEs and SAEs are detailed in the research site's SOPs.

Spontaneously reported or observed AEs will be recorded throughout the study, and AEs will be elicited using a non-leading question at every visit from Screening through the Day 21.

Follow-Up telephone call will assess the status of any AE ongoing at the time of Discharge and record any new AE that has occurred. Regardless of seriousness, intensity, or presumed relationship to the study drug, all AEs will be recorded in the source documentation from the time of first contact with the patient (e.g., Screening) until the end of the Follow-Up Period of the study (Day 21).

AEs that occur after medical Screening and prior to administration of the first dose of study drug will be recorded in the source documentation as Baseline signs and symptoms. All measures required for the management of AEs will be recorded in the source documentation.

7.1 Definitions

7.1.1 Adverse Events

An AE is any untoward medical occurrence in a patient or clinical investigation patient administered a pharmaceutical product and may not necessarily have a causal relationship with the administered treatment. An AE can therefore be any unfavorable and unintended sign (including a clinically significant laboratory abnormality, for example), symptom, or disease temporally associated with the use of a medicinal (investigational) product, regardless of relationship to the medicinal (investigational) product. During the study, an AE can also occur outside the time that the investigational product(s) was given (e.g., during the time from discontinuation of prohibited medications).

Pre-existing conditions, diseases, or disorders are not considered AEs unless there is a change in intensity, frequency, or quality.

7.1.2 Serious Adverse Events and Serious Unexpected Adverse Events

An SAE is any untoward medical occurrence that at any dose

- Results in death,
- Is life-threatening (at the time of the event),
- Requires inpatient hospitalization or prolongation of existing hospitalization,
- Results in persistent or significant disability/incapacity, or
- Is a congenital anomaly/birth defect.

Important medical events that may not result in death, be life-threatening, or require hospitalization may be considered a serious adverse drug experience when, based upon appropriate medical judgment, they may jeopardize the patient and may require medical or

surgical intervention to prevent one of the outcomes listed in this definition. Examples of such medical events include allergic bronchospasm requiring intensive treatment in an emergency room or at home, blood dyscrasias or convulsions that do not result in inpatient hospitalization, or the development of drug dependency or drug abuse.

A serious and unexpected AE is an SAE that is not identified in nature, intensity, or frequency in the risk information set out in the Investigator's Brochure or on the label of the drug.

7.1.3 Clinical Laboratory Abnormalities and Other Abnormal Assessments

Abnormal laboratory findings (e.g., from clinical chemistry or hematology tests or urinalysis) or other abnormal assessments (e.g., from vital signs, ECGs, C-SSRS, 4-Item PSRS, CADSS, COWS) judged as clinically significant by the Investigator or designee will be recorded as AEs or SAEs if they meet the definitions provided in Section 7.1.1 and Section 7.1.2. Furthermore, abnormal laboratory findings or other abnormal assessments present at Baseline that significantly worsen following the start of the study (i.e., become clinically significant) will be reported as AEs or SAEs. However, abnormal laboratory findings present at the start of the study that do not worsen will not be reported as AEs or SAEs.

The Investigator will exercise his or her medical and scientific judgment in deciding whether an abnormal laboratory finding or other abnormal assessment is clinically significant.

7.1.4 Other Adverse Events of Interest

If other AEs of interest are observed during the study, they will be recorded in the eCRFs and analyzed as appropriate in the final clinical study report. Examples of these types of AEs would be difficulty breathing, chest pain, or clinically significant bradycardia, tachycardia, or QTcF prolongation (≥ 500 msec or ≥ 60 msec above the patient's Baseline value that continuously occurs over a period of time). At the discretion of the Investigator, ECGs or other relevant tests may be repeated for confirmation of the results.

If more than one ECG is collected, the mean of the replicate measurements will be reported. If any of the 3 individual ECG tracings has a QTcF value ≥ 500 msec, but the mean of the triplicates is not ≥ 500 msec, the data from the subject's individual tracing will be described in a safety section of the study report to place the ≥ 500 msec value in appropriate clinical context. However, values from individual tracings within triplicate measurements that are ≥ 500 msec will not be included in the categorical analysis unless the average from those triplicate measurements is also ≥ 500 msec. Changes from Baseline will be defined as the change between QTcF post-dose from the time-matched average Baseline triplicates on Baseline Day 1 (Visit 2).

The study drug will be administered under the supervision of study personnel, which should eliminate the opportunity for abuse during the course of the study. However, Investigators should take note of AEs that might suggest that the study drug has the potential for abuse. For example, the occurrence of a euphoria-like response is a key observation in the clinical assessment of whether a test drug has abuse potential.

Examples of Medical Dictionary for Regulatory Activities (MedDRA) Preferred Terms that may provide abuse-related information about a drug include:

- Euphoria-related terms - euphoric mood, elevated mood, feeling abnormal, feeling drunk, feeling of relaxation, dizziness, thinking abnormal, hallucination, inappropriate affect
- Terms indicative of impaired attention, cognition, and mood - somnolence, mood disorders, and disturbances
- Dissociative/psychotic terms - psychosis, aggression, confusion, and disorientation
- Drug withdrawal syndrome

7.2 Evaluation of Adverse Events and Serious Adverse Events

The Investigator or designee is responsible for making an assessment as to the seriousness, intensity, causality, and outcome of an AE.

7.2.1 Classification of Adverse Event Intensity

For each recorded AE or SAE, the Investigator or designee must assess the intensity based on the following criteria (Table 4). If there is insufficient information to determine intensity, the AE must still be reported.

Table 4 Classification of Adverse Event Intensity

Classification	Definition
Mild	An event that is usually transient and may require only minimal treatment or therapeutic intervention. The event does not generally interfere with usual activities of daily living.
Moderate	An event that is alleviated with additional specific therapeutic intervention. The event interferes with usual activities of daily living, causing discomfort, but poses no significant or permanent risk of harm to the subject.
Severe	An event that requires intensive therapeutic intervention. The event interrupts usual activities of daily living or significantly affects clinical status. The event poses a significant risk of harm to the subject and hospitalization may be required.

7.2.2 Classification of Adverse Event Causality

For each recorded AE or SAE, the Investigator or designee must assess the causality based on the following criteria (Table 5) to determine the relationship between the AE and study drug.

Table 5 Classification of Adverse Event Causality

Classification	Definition
Unrelated	The AE or SAE is judged to be clearly and incontrovertibly due only to extraneous causes (e.g., disease, environment) and does not meet the criteria for study drug relationship listed under probable, possible, or unlikely.

Classification	Definition
Unlikely	
The AE or SAE is unlikely related to the study drug, when the AE or SAE:
 
 • Does not follow a reasonable temporal sequence from administration of the study drug. • May readily have been produced by the subject’s clinical state, environmental or toxic factors, or other modes of therapy administered to the subject. • Does not follow a known pattern of response to the study drug. • Does not reappear or worsen when the study drug is re-administered.
Possible	
The AE or SAE is possibly related to the study drug when the connection to the study drug appears unlikely but cannot be ruled out with certainty. This causal relationship is assigned when the AE or SAE:
 
 • Follows a reasonable temporal sequence from administration of the study drug. • May have been produced by the subject’s clinical state, environmental or toxic factors, or other modes of therapy administered to the subject.
Probable	
The AE or SAE is probably related to the study drug when the connection to study drug can be made with a high degree of certainty. This causal relationship is assigned when the AE or SAE:
 
 • Follows a reasonable temporal sequence from administration of the study drug. • Cannot be reasonably explained by the known characteristics of the subject’s clinical state, environmental or toxic factors, or other modes of therapy administered to the subject. • Disappears or decreases upon cessation or reduction in dose (note that there are important exceptions when an AE or SAE does not disappear upon discontinuation of the study drug, yet drug relatedness clearly exists, e.g., bone marrow depression or tardive dyskinesias). • Follows a known pattern of response to the suspected study drug. • Reappears upon re-challenge.

Classification	Definition
Definite	The AE or SAE is definitely related to the study drug when the event: 
 • Follows a reasonable temporal sequence from administration of the study drug. • Follows a known pattern of response to the suspected study drug. • Is confirmed by improvement on stopping and reappearance of the event on repeated exposure to the study drug. • Cannot be reasonably explained by the known characteristics of the subject’s clinical state.

7.2.3 Classification of Adverse Event Outcome

For each recorded AE or SAE, the Investigator or designee must assess the outcome at the time of the last observation. The outcome of AEs or SAEs will be documented as outlined in [Table 6](#).

Table 6 Classification of Adverse Event Outcomes

Classification	Definition
Fatal	The subject died.
Resolved	The AE or SAE has ended.
Resolved with Sequelae	The AE or SAE has ended but changes are noted from Baseline.
Unresolved	The AE has not ended. An AE outcome can only be categorized as unresolved, if the AE is: 
 • Ongoing at the end of the reporting period (i.e., 14 days after the last dose of study drug on Day 7), and the Investigator deems that further follow-up is not medically required. • Lost to follow-up after repeated unsuccessful attempts to contact the subject. • Ongoing and referred to the subject’s physician or a specialist for follow-up.

7.3.2 Any Adverse Event

Regardless of seriousness, intensity, or presumed relationship to study drug, all AEs will be recorded in the source documentation. When the signs and symptoms are due to a common etiology, the diagnoses will be recorded whenever possible. In addition, the Investigator must record his or her opinion as to the intensity of the AE and whether the AE is related to the study drug. All measures required for management of the AE will be recorded in the source documentation.

7.3.3 Pregnancy

Given that the effects of the study drug on egg and sperm have not been fully elucidated, any pregnancy in the patient or partner of a patient participating in the study will be reported to Relmada within **24 hours** of learning of the event.

Follow-up information will be obtained where possible (i.e., with the consent of the patient or patient's partner) regarding the course and outcome of the pregnancy, including any post-natal sequelae in the infant.

7.4 Follow-Up of Adverse Events and Serious Adverse Events

All unresolved AEs will be followed for up to a minimum of *14 days* after the patient's final dose of study drug on Day 7 unless the Investigator's judgment dictates otherwise, the event has resolved or stabilized before Day 21, or the patient is lost to follow-up.

All AEs that result in discontinuation and all SAEs will be followed until one of the following occurs:

- The event resolves.

- The event stabilizes.
- The event returns to a Baseline value, if a Baseline value is available.
- The event can be attributed to agent(s) other than the study drug or to factors unrelated to study conduct.

When it becomes unlikely that any additional information can be obtained (e.g., patient or health care practitioner refuses to provide additional information, the patient is lost to follow-up), the Investigator or designee will ensure that the follow-up includes any pertinent supplemental investigations (e.g., laboratory tests or investigations, histopathological examinations, or consultation with other health care professionals) to elucidate the nature and/or causality of the AE or SAE.

Investigators are not obligated to actively seek AEs or SAEs in former study patients that occur after the Follow-Up Period. However, if the Investigator or designee learns of any AE or SAE at any time after a patient has been discharged from the study and the event is considered as reasonably related to the study drug, the Investigator will notify Relmada.

8 DATA ANALYSIS AND STATISTICAL CONSIDERATIONS

8.1 Statistical and Analytical Plans

8.1.1 Analysis Populations

The study analysis populations will consist of

- Randomized population: All patients who are randomized.
- Safety population: All randomized patients who receive any study treatment (REL-1017 or Placebo).
- Pharmacokinetic population: All patients who receive REL-1017, with at least 1 post-dose blood draw to determine plasma concentration of d-methadone. Pharmacokinetic parameters will be reported for this population where available.
- Intent-to-Treat population: All randomized patients who receive any study treatment (REL-1017 or Placebo) and have a Baseline and at least 1 post-Baseline efficacy measurement (MADRS, SDQ, CGI-S, or CGI-I).

The details of patient evaluability criteria will be determined prior to study unblinding.

8.1.2 General Statistical Considerations

Complete details of the statistical analyses to be performed will be documented in a Statistical Analysis Plan (SAP) that will be completed prior to unblinding the study data. This document will include more details of the analysis populations, summary strategies, and any amendments to the proposed analyses listed here, if necessary. Any changes to the SAP will be outlined in the final clinical study report.

8.1.3 Endpoint Definitions

8.1.3.1 Primary Endpoint: Safety and Tolerability of REL-1017

The primary objective is to evaluate the safety and tolerability of 7 days of daily dosing with REL-1017 25 mg or 50 mg in patients. The following assessments will be conducted to measure safety and tolerability throughout the study:

- AEs
- Vital signs
- Weight
- Physical examination
- Clinical laboratory parameters (chemistry, hematology, and urinalysis)
- Electrocardiogram (ECG) parameters
- Columbia-Suicide Severity Rating Scale (C-SSRS)
- Clinician Administered Dissociative States Scale (CADSS)

- Clinical Opiate Withdrawal Scale (COWS)
- 4-Item Positive Symptoms Response Scale (4-Item PSRS)

8.1.3.2 Secondary Objective: Pharmacokinetic Profile of REL-1017

A secondary objective is to evaluate the PK profiles of 7 days of daily dosing with REL-1017 25 mg and 50 mg on Day 1 through Day 7, Day 8, Day 9, and Day 14 where data allow. The plasma concentration of d-methadone as a function of time will be analyzed using non-compartmental, validated software to estimate the following PK parameters:

- Maximum observed plasma concentration (C_{max})
- Time to maximum observed plasma concentration (T_{max})
- Area under the plasma concentration-time curve from time zero until the dosing interval of 24 hours (AUC_{tau})
- Area under the plasma concentration-time curve from time zero until the last quantifiable time point (AUC_{0-last})
- Area under the plasma concentration-time curve from time zero to infinity (AUC_{0-inf})
- Apparent termination elimination rate constant (λ_z)
- Apparent terminal elimination half-life ($t_{1/2}$)
- Attainment of steady state
- Steady state clearance (C_{SS}/F)
- Volume of distribution at steady state (V_{SS}/F)
- Accumulation ratios based on minimum observed plasma concentration (C_{min}), C_{max} , and AUC_{tau}

In addition, other relevant parameters may be calculated.

8.1.3.3 Secondary Objectives: Efficacy of REL-1017

The efficacy of 7 days of daily dosing with REL-1017 25 mg and 50 mg as measured by the following efficacy endpoints:

- Change from Baseline (Day 1) to EDP (Day 7) on the MADRS with measurements made pre-dose on Day 1 and Day 2; post-dose on Day 4 and Day 7 within 3 hours of dosing; and on Day 14;
- Change from Baseline (Day 1) to EDP (Day 7) on the SDQ with measurements made pre-dose on Day 1 and Day 2; post-dose on Day 4 and Day 7 within 3 hours of dosing; and on Day 14;

- Change from Baseline (Day 1) to EDP (Day 7) on the CGI-S with measurements made pre-dose on Day 1 and Day 2; post-dose on Day 4 and Day 7 within 3 hours of dosing; and on Day 14.
- Evaluation of CGI-I total score on Day 7 (post-dose), as well as CGI-I scores on Days 2 (pre-dose), 4 (post-dose), and 14.

8.1.4 Planned Analyses

All analyses (other than PK parameter calculations) will be performed using SAS Version 9.3 or higher, run on the Microsoft Windows Server 2003 R2 operating system. Pharmacokinetic parameter calculations will be performed using WinNonlin Version 6.3 or higher, run on the Windows XP platform or higher.

8.1.4.1 Analysis of Safety Assessments

Safety and tolerability parameters will be listed by treatment and patient and displayed in summary tables using descriptive statistics.

8.1.4.2 Adverse Events

Original terms used in the eCRFs by Investigators or designees to identify AEs will be coded using the MedDRA (Version 16.0 or higher). The number and percentage of patients with treatment-emergent AEs will be summarized by system-organ-class, preferred term, and treatment and for each treatment by maximum severity and relationship to study treatment. A treatment-emergent AE is any that is new in onset or was aggravated in severity or frequency following the first dose of study drug (Day 1), up to and including the last visit of the study (Day 21).

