
Study Drug, Dose Schedule, and Mode of Administration:
	
REL-1017 consists of d-methadone hydrochloride (HCl) in a powder formulation. The following doses will be used in the study:
 
 • REL-1017 75 mg QD Day 1, 25 mg REL-1017 QD Day 2-7 • REL-1017 100 mg QD Day 1, 50 mg REL-1017 QD Day 2-7 • Placebo (Ocean Spray® Diet Cranberry Juice) 
REL-1017 will be provided as a powder and prepared as a solution with Ocean Spray® Diet Cranberry Juice on site to obtain a final volume of 100 mL for dosing.
 
Patients will continue to take the same, stabilized antidepressant medication that they were taking at Screening throughout the course of the study, and the supply of medication during the confined study period will be arranged and assured by the Investigator.
 
An unblinded pharmacist will assign study drug to patients according to randomized treatment codes provided by the Interactive Web Response System (IWRS). The randomization code used in the IWRS will be prepared by a statistician who is not working as a statistician on the study in any other capacity. The study drug solution or Placebo will be prepared within 3 hours of administration in blinded containers, and then will be dispensed to blinded study staff for administration to the patients.
 
After drinking the 100 mL of study drug, 25 mL of non-carbonated water will be added to the study drug container and gently swirled. The patient will drink this rinse volume followed by 125 mL of non-carbonated water to drink immediately thereafter.
 
All dosing must be completed within 5 minutes.
 
Dosing will take place once daily in the morning after an overnight fast of at least 8 hours.

Study Population and Duration of Participation
	
Adult patients with MDD who are diagnosed with a current major depressive episode (MDE) and who have experienced an inadequate response to 1 to 3 courses of treatment with an adequate dose and duration (as defined by the Antidepressant Treatment Response Questionnaire [ATRQ]) of an antidepressant medication for the current episode will be randomized to study drug in a 1:1:1 ratio.
 
Approximately 120 patients will be screened, and approximately 60 qualified patients will be randomized to study drug in a 1:1:1 ratio (approximately 20 patients per arm). Each patient will participate for up to 51 days (30 days Screening, 7 days treatment, and 14 days of observation and follow-up).

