1.2.1 Results from Clinical Study REL-1017-111

Study REL-1017-111 was “A Phase 1 Study to Investigate the Safety, Tolerability, and Pharmacokinetic Profile of Single Ascending Doses of d-Methadone in Healthy Subjects.” It was a double-blind, randomized, placebo-controlled study in sequential arms. Safety and PK for REL-1017 (d-methadone) oral administration were determined in ascending dose arms from 5 mg to 200 mg. Pharmacokinetic parameters were calculated for all dose levels, although some individual results had to be excluded due to emesis or statistical analysis criteria.

Pharmacogenomics analysis was performed for subjects exhibiting either fast or slow metabolism of REL-1017. Overall, there were minimal subjective PD effects of REL-1017 up to 150 mg, as assessed by the Bond-Lader VAS. For additional information, please reference the Investigator's Brochure.

The overall conclusions drawn from Clinical Study REL-1017-111 were:

- The MTD for oral REL-1017 in healthy opiate-naive subjects was determined to be 150 mg.
- The PK analysis revealed high variability of the REL-1017 parameters, including C_{max} , time to maximum observed plasma concentration (T_{max}), area under the plasma concentration-time curve from time zero to infinity (AUC_{0-inf}), apparent terminal elimination half-life ($t_{1/2}$), and apparent clearance/bioavailable fraction absorbed (CL/F).
- Statistical models demonstrated linear proportionality of C_{max} and AUC_{0-inf} versus dose, although the result was not statistically significant.
- In general, there were no specific trends observed for T_{max} or $t_{1/2}$ of REL-1017.
- The subjective PD effects of REL-1017 up to 150 mg were minimal.
- The objective measure of PD effects, pupillometry, showed a dose response with greater pupil constriction in the higher dose groups.
- The single doses of REL-1017 administered in this study appeared to be safe with no indication of respiratory depression or clinically significant QTcF prolongation. In terms of tolerability, nausea and vomiting become potential adverse events (AEs) with higher doses.

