2 STUDY OBJECTIVES

2.1 Primary Objective

The primary objective of this study is safety:

Safety objectives will assess the safety and tolerability of 25 mg and 50 mg of REL-1017 (d-methadone) compared to Placebo as adjunctive treatment in patients with MDD. The following assessments will be conducted to measure safety and tolerability throughout the study:

- AEs
- Vital signs
- Weight
- Physical examination
- Clinical laboratory parameters (chemistry, hematology, and urinalysis)
- Electrocardiogram (ECG) parameters
- Columbia-Suicide Severity Rating Scale (C-SSRS)
- Clinician Administered Dissociative States Scale (CADSS)
- Clinical Opiate Withdrawal Scale (COWS)
- 4-Item Positive Symptom Rating Scale (4-Item PSRS)

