4 STUDY POPULATION

4.1 Number of Patients

Adult patients with MDD who are diagnosed with a current MDE and who have experienced an inadequate response to 1 to 3 courses of treatment with an adequate dose and duration (as defined by the ATRQ) of an antidepressant medication for the current episode will be randomized to study drug in a 1:1:1 ratio. Approximately 20 patients each will receive REL-1017 75 mg/REL-1017 25 mg, REL-1017 100 mg/REL-1017 50 mg, or Placebo.

Investigators should strive to evenly distribute the choice of ADTs at their respective sites among different ADTs. No more than 2 out of every 6 patients at an investigational site should be assigned to any 1 ADT without permission by the Medical Monitor.

Approximately 120 patients will be screened, and approximately 60 qualified patients will be randomized to study drug in a 1:1:1 ratio (approximately 20 patients per arm). Each patient will participate for up to 51 days (30 days Screening, 7 days treatment, and 14 days of observation and follow-up).

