5.3 Method of Assigning Patients to Treatment Groups

Randomization will be used to avoid bias in the assignment of patients to treatment, to increase the likelihood that known and unknown patient attributes (e.g., demographics and Baseline characteristics) are evenly balanced between treatment groups, and to enhance the validity of statistical comparisons between treatment groups.

Each potential patient will be assigned a unique number in the Screening process (Patient ID Number). This number will be used to identify the patient throughout the study. Patients who are randomized will be assigned a unique randomization number. Once any patient number is assigned, it cannot be reassigned to any other patient.

All randomization codes will be generated by the designated unblinded statistician at Syneos Health, Inc., (formerly INC Research, Inc.) before the start of the study. The treatment assignment for each subject will be assigned through the IWRS in a 1:1:1 ratio (REL-1017 25 mg, REL-1017 50 mg, or Placebo). Stratified randomization will be used to achieve a reasonable balance of patients taking cytochrome (CYP) 2B6 inhibitor ADTs versus patients who

take non-CYP2B6 inhibitors within the three treatment groups. A randomization list will be computer-generated for each of the two strata using random permuted blocks (first strata: patients receiving concomitant ADTs that are cytochrome CYP2B6 inhibitors: paroxetine, fluoxetine, sertraline; second strata: patients receiving concomitant ADTs that are not CYP2B6 inhibitors). The goal of stratified randomization is to end the study with a similar number of patients taking CYP2B6 inhibitors in each study treatment group (e.g., if 15 patients are randomized who are taking ADTs with CYP2B6 inhibitor activity, then approximately 5 will be in the REL-1017 25 mg group, 5 will be in the REL-1017 50 mg group, and 5 will be in the Placebo group). Stratification will allow for subgroup exploratory analyses to be interpreted more easily after the study is complete and unblinded.

If applicable, replacement patients for patients who withdraw prior to dosing will receive the same treatment allocation as those whom they replace.

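### The planned adverse event tables label the arms 25 mg and 50 mg but do not show whether events followed the 75/100 mg Day 1 dose, arose on the 25/50 mg days, or began after dosing ended

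*Combined protocol and SAP*

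**What the plan says.** **Objective.** Section 2.1 states: "Safety objectives will assess the safety and tolerability of 25 mg and 50 mg of REL-1017 (d-methadone) compared to Placebo". Section 8.1.3.1 repeats this as the aim to "evaluate the safety and tolerability of 7 days of daily dosing with REL-1017 25 mg or 50 mg in patients". Neither mentions 75 mg or 100 mg.

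**Dosing.** The Synopsis (study drug and dose schedule) gives the two active regimens as "REL-1017 75 mg QD Day 1, 25 mg REL-1017 QD Day 2-7" and "REL-1017 100 mg QD Day 1, 50 mg REL-1017 QD Day 2-7". Section 3.2 agrees.

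**Adverse event summary.** Under Section 8.1.4.2 an event is treatment-emergent if it is new or aggravated "following the first dose of study drug (Day 1), up to and including the last visit of the study (Day 21"). Patients with such events are counted by coded term and treatment, and within each treatment by worst severity and by relationship. Neither that section nor the Synopsis describes a table by day, period or dose at onset.

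**Labels.** Section 5.3 assigns patients "in a 1:1:1 ratio (REL-1017 25 mg, REL-1017 50 mg, or Placebo"), and Section 8.1.5 uses the same short labels. Section 4.1 names the full regimens: "Approximately 20 patients each will receive REL-1017 75 mg/REL-1017 25 mg, REL-1017 100 mg/REL-1017 50 mg, or Placebo".

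**Contrast.** Section 8.1.4.3 summarises vital signs, ECG and laboratory results by scheduled time. Section 8.1.4.1 plans listings by patient, and Section 8.1.2 leaves further detail to an SAP completed before unblinding.

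**The concern.** Read as written, the adverse event tables report under 25 mg an event that followed a 75 mg dose, and under 50 mg one that followed 100 mg. They report in the same way an event that began up to 14 days after the last dose. A patient who takes only the Day 1 dose and stops is in the Safety population (Section 8.1.1), is not replaced (Section 4.5), and is counted under a daily dose never taken.

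The protocol gives a reason why timing may matter. Section 1.2.1 concludes from the single-dose study that "nausea and vomiting become potential adverse events (AEs) with higher doses". Adverse events are the first-listed measure of the primary objective, and a reader of the study report will take a row headed 25 mg as evidence about 25 mg. At stake is how the adverse event result is attributed. The randomised comparison itself is not in question.

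**Working it through.** **1. The plan's own figure.** Section 4.1 gives up to 51 days: 30 + 7 + 14 = 51, reproduced. Follow-up after the last dose is 21 − 7 = 14 days. The treatment-emergent window is 1 + 6 + 14 = 21 nominal days.

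**2. Make-up of the window and of the dose.** The documents' doses are used, with the lower dose on Days 2-7.

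| | Arm 1 | Arm 2 | Ratio, Arm 2 / Arm 1 |
|---|---|---|---|
| Day 1 (1/21 = 4.8% of days) | 75 mg | 100 mg | 1.33 |
| Days 2-7 (6/21 = 28.6%) | 6 × 25 = 150 mg | 6 × 50 = 300 mg | 2.0 |
| Days 8-21 (14/21 = 66.7%) | none given | none given | – |
| Total | 225 mg | 400 mg | 1.78 |
| Day 1 share of dose | 75/225 = 33.3% | 100/400 = 25.0% | |

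The pooled contrast between the active arms is therefore not a pure 25 mg against 50 mg contrast. Shares of days are not shares of events; the documents give no event rates.

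**3. Can the pooled table tell the patterns apart?** All risks here are assumptions. Take a background of 1% per day in every arm, with drug-added risk d1 on Day 1 and dm over Days 2-7.

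- Placebo, pooled: 1 − 0.99^21 = 19.0%.
- Drug, pooled: 1 − 0.99^21 × (1 − d1)(1 − dm).
- Drug, Days 2-7 only: 1 − 0.99^6 × (1 − dm).

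| Pattern | Pooled, drug | Pooled, placebo | Days 2-7, drug |
|---|---|---|---|
| d1 = 30%, dm = 10% | 49.0% | 19.0% | 15.3% |
| d1 = 10%, dm = 30% | 49.0% | 19.0% | 34.1% |

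The pooled rows are identical because (1 − d1)(1 − dm) is the same product in either order. The planned table cannot distinguish the two patterns; an onset-period table can.

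**4. Effect of the 14 days after dosing.** If risk in those days is the same in all arms, the pooled risk difference for any event shrinks by 1 − (1 − b)^14, where b is the daily background risk. For b = 0.5%, 1%, 2% and 4% this is 7%, 13%, 25% and 44%.

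**5. How far a split by day separates the doses.** Section 1.2.2 reports steady state by Dose 7 at 25 mg and 50 mg, which is 6 × 24 = 144 h after the first dose. No half-life is stated. Assume one-compartment decay and that 144 h equals 3.3 to 5 half-lives.

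- Half-life h: 144/5 = 28.8 h to 144/3.3 = 43.6 h.
- Accumulation 1/(1 − 2^(−24/h)): 2.28 to 3.15.
- First dose relative to steady state on the labelled dose: Arm 1, 3/3.15 to 3/2.28 = 0.95 to 1.32; Arm 2, 2/3.15 to 2/2.28 = 0.63 to 0.88.
- Remaining 48 h after the last dose: 32% to 47%; at 168 h: 2% to 7%.

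On this assumption, the 3-fold and 2-fold dose ratios on Day 1 overstate the difference in exposure, drug from Day 1 is present in the following days, and drug persists after the last dose.

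**The case against.** The case against is substantial, and most of it limits the point without removing it.

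- **The trial still has information on its primary question.** Adverse events are one of ten listed safety assessments. Vital signs, ECG and laboratory data are shown by time point, and CADSS and the 4-Item PSRS are measured 2 hours after dosing on both Day 1 and Day 7. A reader might infer that the trial cannot say whether 25 mg or 50 mg was tolerated. The documents do not support that. The limitation lies in the planned adverse event tables.
- **Withdrawal has its own instrument.** COWS is measured on Days 8, 9 and 14, and Section 7.1.4 lists a withdrawal term for attention. It would be wrong to conclude that withdrawal cannot be separated at all. COWS does not, however, divide adverse events by period.
- **The weeks after dosing are not drug-free.** PK sampling runs to Day 14, and the assumed decay above leaves drug on board. Keeping later events in the treatment-emergent set is reasonable; they lack only a separate display.
- **The loading dose is openly part of each regimen**, and Section 5.4 reports single doses up to 150 mg as well tolerated. Section 1.2.1 gives no threshold for nausea and vomiting in a study that reached 200 mg. Event rates after Day 1 may be low.
- **The SAP may add the split, and listings would allow it later.** Both are true. Nothing in the text commits to it, and with about 20 patients per arm, period limits chosen after unblinding would carry less weight than prespecified ones.
- **A split cannot isolate 25 mg or 50 mg.** This stands, and the tables should say so.

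**Conclusion.** The point holds as a gap in planned reporting. The stated objective names 25 mg and 50 mg, the regimens start at 75 mg and 100 mg, and the adverse event tables described merge three phases under the short labels. The comparison of each whole regimen with placebo remains valid. The tables cannot show which phase the events belong to: in the illustration, one pooled result is compatible with 15.3% or 34.1% on the 25/50 mg days. That size rests on assumed risks. The carry-over figures rest on an assumed half-life. The day and dose counts follow directly from the documents, given the lower dose on Days 2-7.

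This is an inexpensive improvement that serves the primary objective. It is not a defect that invalidates the safety assessment, and the Day 1 dose ratios should not be read as exposure ratios.

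**What to change.** In Section 8.1.4.2 and the SAP, before unblinding:

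1. Keep the overall treatment-emergent table.
2. Add tables by arm and onset period, each with its at-risk count: from the Day 1 dose to just before the Day 2 dose; from the Day 2 dose to a stated lag after the last dose; and from then to Day 21.
3. Label the arms 75/25 mg and 100/50 mg throughout, as Section 4.1 does.
4. State with the tables that Day 1 drug carries over into the second period and that drug persists after the last dose, so the split describes timing and does not isolate a dose.
5. Confirm that the eCRF records the clock time of adverse event onset, which the text does not state; otherwise define the periods by date.
6. Before setting the limits, reconcile Section 5.1, which heads the lower doses Day 2-6, with the Synopsis and Sections 3.2 and 5.4, which give Day 2-7.

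The cost is SAP wording and a few table shells. The downside is sparse cells at about 20 patients per arm, so the added tables should remain descriptive. No dose or clinical procedure changes.
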